#### **17.4.5 Quality of life**

Quality of Life will be assessed using the patient-reported outcome measures: EORTC-QLQ-C30, EORTC-QLQ-CLL and EQ-5D-5L. This will be assessed at clinic visits or via questionnaires, completed at baseline and then at the time-points detailed in Section 13 and Appendix 4.

#### **17.4.6 Summative treatment-free Interval**

This is defined as the time to treatment strategy failure, excluding any time spent on treatment. This is equivalent to the total time spent on trial minus the total time spent on treatment. Alternatively the sum of all treatment-free intervals. For example, for a participant on the intermittent strategy, this is their time on trial minus any time spent on treatment due to hitting the restart criteria, whereas for a patient in the continuous strategy, this is the time spent off treatment (for example, due to toxicity breaks) whilst on trial. If a participant does not experience treatment failure or death during the trial they will be considered censored at the time of analysis.

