### 8.1 Overall design and plan of the study

The 'Randomisation Pathway' is designed as a prospective, multicentre, open-label, randomised, controlled, 2-arm, parallel-group, non-inferiority study to compare an intermittent treatment strategy (experimental arm) with continuous treatment (control arm) with ibrutinib for patients with CLL who have responded well to treatment with ibrutinib. The primary outcome for this pathway will be time to treatment strategy failure, defined as the first documented instance of active disease as defined by the 2018 iwCLL criteria (Appendix 1) that does not respond to treatment, or death from any cause.

At randomisation previously treated participants will have been receiving ibrutinib as their second- or subsequent-line of therapy for at least the previous 36 months, whilst front-line participants entering from the FLAIR trial will have received 6 years of treatment with ibrutinib. There is no restriction on maximum duration of treatment for the previously treated cohort prior to enrolment. The recruitment period is 6 years, and each participant will be followed up for at least 3 years after randomisation. Participants will receive treatment during the trials 6 year recruitment period and for the 3 years of follow up, meaning that participants will be on the trial for between 3-9 years, depending upon when they enter the trial. 800 patients will be entered into the Randomisation Pathway with the goal of observing 379 treatment failure or death events.

Participants will be randomised to either an intermittent treatment strategy or to continuous therapy. Treatment allocation (1:1) will be by minimisation with a random element incorporating the following three factors: centre, whether or not the participant was previously treated in FLAIR and minimal residual disease (MRD) level at randomisation.

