#### **19.4.5 Summative Treatment-free Interval**

This is defined as the time to treatment strategy failure, excluding any time spent on treatment. This is equivalent to the total time spent on trial minus the total time spent on treatment. Alternatively the sum of all treatment-free intervals. In addition, the median summative time on treatment annually post randomisation will be estimated using the Kaplan-Meier method. By design this endpoint should confirm compliance with the intermittent strategy by showing superiority in the intermittent strategy when compared to the continuous strategy with respect to more time spent off treatment.

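### Treating accumulated time off (or on) ibrutinib as a censored time to failure makes calendar-time censoring informative; Kaplan-Meier-type estimates are biased, most of all for treatment-free time in the continuous arm

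*Protocol*

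**What the plan says.** Section 17.4.6 gives the definition: "This is defined as the time to treatment strategy failure, excluding any time spent on treatment". The same measure applies to both arms. In the pausing arm it is trial time minus re-treatment; "whereas for a patient in the continuous strategy, this is the time spent off treatment (for example, due to toxicity breaks) whilst on trial". The event is failure or death, and everyone else is handled by one rule: "If a participant does not experience treatment failure or death during the trial they will be considered censored at the time of analysis".

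Section 19.4.5 repeats the definition and states that "the median summative time on treatment annually post randomisation will be estimated using the Kaplan-Meier method". It gives the purpose as confirming compliance, by "showing superiority in the intermittent strategy when compared to the continuous strategy with respect to more time spent off treatment". No estimator is named for the treatment-free interval itself.

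On follow-up, section 8.1 says: "The recruitment period is 6 years, and each participant will be followed up for at least 3 years after randomisation".

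**The concern.** Administrative censoring between 3 and 9 years can reasonably be taken as independent of failure in calendar time. It does not stay independent on an accumulated clock. There, the censoring value is follow-up multiplied by the participant's own rate of accruing off-drug (or on-drug) time, and that rate is what the endpoint measures. Slow accruers are censored at small values and fast accruers at large ones, so those still at risk at a given accumulated time do not represent those who have left.

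The continuous arm shows this most sharply. A participant who never interrupts treatment has the value zero, as a failure or as a censoring. The Kaplan-Meier curve drops at zero only for the failures. The censored zeros leave the risk set and are in effect assumed to go on to have the off-drug time of participants who did take breaks.

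At stake is a secondary endpoint meant to show that the strategies were delivered as planned. A reader could be told that the typical continuous participant spent weeks off drug when the typical value is none, or that the pausing arm used more drug than it did.

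**Working it through.** **Inputs from the protocol.** Failure times (18.1): 45% with median 10 years, 55% with median 4 years, both exponential; dropout 5%; 379 events. Size (8.1): 800 randomised. Follow-up: 3 to 9 years. Minimum re-treatment before another pause: 12 months (13.8.3). Break frequency, break length and their spread between participants are not given, so they are assumptions, shown as ranges.

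**Reproducing the plan's figures.** S(t) = 0.45 × 0.5^(t/10) + 0.55 × 0.5^(t/4). At t = 5.84 this is 0.300 + 0.200 = 0.500, the stated median. With uniform accrual over 6 years and 3 more years of follow-up, the average of S over 3-9 years is 0.502. Expected events are 800 × 0.498 = 398, or 378 from 760 after 5% dropout, against 379 stated. About half of participants are therefore censored.

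**A limiting case by hand.** Suppose no continuous participant ever takes a break. Every treatment-free value is zero. Kaplan-Meier at zero is 1 − (failures at zero)/n = 1 − 0.498 = 0.502. The estimator reports 50% of the arm above zero; the truth is 0%. The figure is simply the share censored, so it depends on when the analysis is done.

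**Continuous arm, simulated.** 40,000 participants per scenario. Those who ever break have 0.4 breaks a year averaging 3 weeks.

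| Never break | Observed zero | True P(>0) | Kaplan-Meier P(>0) | True median (weeks) | Kaplan-Meier median (weeks) |
|---|---|---|---|---|---|
| 20% | 43% | 0.62 | 0.73 | 2.7 | 6.1 |
| 40% | 57% | 0.46 | 0.67 | 0 | 4.7 |
| 60% | 72% | 0.31 | 0.61 | 0 | 3.3 |
| 80% | 86% | 0.15 | 0.56 | 0 | 1.6 |

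In the last row, failures at zero are 1 − 0.556 = 0.444 of the arm and censored zeros are 0.856 − 0.444 = 0.412. That second group is what the curve wrongly carries above zero. If software discards zero times, the median becomes about 12-13 weeks. With a different assumption (80% without breaks, the rest with 0.05-0.5 years off), Kaplan-Meier gives 57-60% above zero against 17-20%, and a median of 0.16-0.20 years against zero.

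**Pausing arm, time off treatment.** With an assumed median break of about 3 years and between-participant log-SD from 0 to 1.2, the true median is 3.8-4.4 years and the Kaplan-Meier median 4.2-4.5 years. Bias runs from about 0% with no heterogeneity to 4.26/3.77 − 1 = +13%.

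**Pausing arm, time on treatment.** This is the quantity for which Kaplan-Meier is named. With half the arm at a median break of 1 year, half at 5 years, and at least 12 months' re-treatment, the Kaplan-Meier median is 1.99 years against a true 1.46, or 1.99/1.46 − 1 = +36%. With 12-18 months' re-treatment it reached +88%. Where break lengths are alike across participants it is about 0%.

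**Dependence.** Among censored participants, off-drug time at censoring correlates with final off-drug time at 0.17-0.43 (pausing) and 0.47-0.64 (continuous).

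**The case against.** Five points can be made for the plan.

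- **Kaplan-Meier is not named for the treatment-free interval.** True. Section 19.4.5 attaches it to time on treatment; its use for the treatment-free interval is inferred from the censoring rule in 17.4.6. But that rule already fixes a failure event and censoring on an accumulated clock, so the problem is more than detail left to the analysis plan, and it also affects the quantity for which Kaplan-Meier is named.
- **In the continuous arm, time on treatment is nearly calendar time.** True, so censoring there is close to independent and that one estimate is nearly unaffected. The pausing arm does not have this protection.
- **The word annually may mean yearly calendar summaries.** Possible, and such summaries would be sound, but the sentence asks for a Kaplan-Meier median.
- **The contrast is years against weeks.** True. No plausible bias of this kind reverses it.
- **The break patterns are assumed.** True. The sizes are ranges; the mechanism and the limiting case do not depend on them.

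Two stronger readings are tempting and not supported. A reader might infer that the estimates are meaningless in both arms. That fits only the continuous-arm treatment-free curve; in the pausing arm the treatment-free median is at most modestly high. A reader might also set a Kaplan-Meier restricted mean to 5 years of accumulated off-drug time against mean off-drug time in the first 5 calendar years and call the gap bias. In one run these were 3.41 and 2.83 years, but the true value on the accumulated scale was 3.39. Almost all of that gap is a change of scale.

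**Conclusion.** The defect is real and lies in the protocol text. Calendar censoring is dependent by construction on either accumulated clock. For continuous-arm treatment-free time the curve mainly reflects the split between failures and censorings, and its median does not describe the typical participant. Pausing-arm treatment-free medians are little affected (about 0 to +13%), while pausing-arm time on treatment can be materially overstated (0% to about +90%). These sizes rest on the protocol's failure model, 3-9 years of follow-up and assumed break and re-treatment patterns.

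The consequence is limited. This is a secondary endpoint used to confirm compliance, the direction of the arm difference would stand, and the sample size and primary analysis are unaffected. It should be corrected, but nothing else depends on it.

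**What to change.** In 17.4.6 and 19.4.5, replace the censored-time definition and the Kaplan-Meier median with mean time off treatment, and mean time on treatment, accrued within a fixed horizon from randomisation and counted to failure or death.

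- Use 36 months as the main horizon. With at least 3 years' planned follow-up it is nearly fully observed apart from dropout (5% assumed in 18.1).
- For later horizons, use the area under the calendar-time curve of being failure-free and off ibrutinib, and the matching curve for on ibrutinib. Calendar censoring can be treated as independent on that scale.
- Give the arm difference with a bootstrap confidence interval.
- Reconcile 19.4.5, whose heading and superiority aim concern time off treatment while its estimator sentence concerns time on treatment.

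Under the assumptions above, the 36-month means would be about 2.0-2.3 years (pausing) against 0.6-2.3 weeks (continuous), so the compliance message remains plain. The cost is protocol and analysis-plan wording, a little more analysis work, and an estimand limited to the chosen horizon. No new data are needed.

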#### **17.4.7 Response to Re-Treatment in Intermittent Arm**

Objective response rate is defined as a categorical outcome consisting of whether a participant had partial remission (PR), stable disease (SD) or progressive disease (PD) according to the response criteria defined by the standard 2018 iwCLL criteria (Appendix 1) between 9 and 12 months after restarting ibrutinib. To avoid mandating bone marrow biopsies, CR and CRi will not be an outcome, where they are reported due to local practice they will be included as PR.

#### **17.4.8 Time to Next Treatment for CLL**

Time to next treatment is defined as the time from randomisation to the start date of the next line of treatment. Participants who have died post cessation of ibrutinib but before taking up a new treatment

will be censored. Participants not known to have received another treatment for CLL at the time of the analysis will be censored at the last date they were known to be alive or dead without confirmed progression. Additionally if the participant switches to an alternative irreversible BTK inhibitor such as acalabrutinib or zanubrutinib, this will not be considered a new line of treatment, for this endpoint. These participants will be considered censored from the time of their switch.

For the Clinical Need Cohort, this will be time from registration to the start date of the next line of treatment.

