#### **19.4.7 Time to next treatment for CLL**

Time from randomisation to next treatment after the cessation of trial treatment will be analysed using Cox regression analysis accounting for the stratification factors (excluding centre), and Kaplan-Meier curves will be presented. This analysis will seek to show the superiority of the intermittent strategy in this endpoint.

This endpoint, measuring time from registration, will also be summarised with Cox's regression and a Kaplan-Meier curves for the participants in the Clinical Need Cohort, stratified by MRD level, available from FLAIR.

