#### **5.6. Time to next treatment, progression-free survival, event-free survival, and overall survival**

Progression-free survival is defined as the interval between the first treatment day (in phase 3 trials: day of randomization for intent-to-treat analysis) to the first sign of disease progression or death from any cause. Event-free survival is defined as the interval between the first treatment day (in phase 3 trials: day of randomization for intent-to-treat analysis) to the first sign of disease progression or start of a new treatment or death (whichever occurs first). Overall survival is defined as the interval between the first treatment day (in phase 3 trials: day of randomization for intent-to-treat analysis) to death. Time to next treatment is defined as interval between the first treatment day until the patient starts an alternative therapy for progressive CLL.

Note that the response duration may be assessed during therapy for continuous treatment, in particular with oral agents, as well as after the end of treatment, in particular with chemo(immuno)therapy. Study protocols should provide detailed specifications of the planned time points for the assessment of the treatment response under continuous therapy. Response durations <6 months are not considered clinically relevant (see refractory disease, section 5.8).

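### Time to next treatment censors deaths and is shown by Kaplan-Meier, so its curves overstate the probability of receiving next treatment and its hazard ratio is silent on deaths

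*Protocol*

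**What the plan says.** Protocol 17.4.8 gives the endpoint a single event: "Time to next treatment is defined as the time from randomisation to the start date of the next line of treatment". Two sentences deal with participants who never reach it. The first censors "Participants who have died post cessation of ibrutinib but before taking up a new treatment". The second says that those not known to have had another CLL treatment "will be censored at the last date they were known to be alive or dead without confirmed progression". Together they cover deaths after stopping ibrutinib and deaths without progression. Neither kind is an event.

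Protocol 19.4.7 fixes the method, Cox regression with Kaplan-Meier curves, and the aim: "This analysis will seek to show the superiority of the intermittent strategy in this endpoint". Section 19.4 sets a 2.5% significance level for secondary analyses unless stated otherwise. For the non-randomised group, the endpoint "will also be summarised with Cox's regression and a Kaplan-Meier curves for the participants in the Clinical Need Cohort".

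By contrast, death from any cause is an event in the primary endpoint (17.4.1) and in overall survival (17.4.2). The response criteria reproduced in Appendix 1 (5.6) read: "Time to next treatment is defined as interval between the first treatment day until the patient starts an alternative therapy for progressive CLL". They do not mention death, so 17.4.8 does not contradict the appendix.

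**The concern.** Death before next treatment rules the event out; it does not merely leave it unobserved. Kaplan-Meier treats a censored participant as still able to have the event later, at the rate seen in those who remain. One minus Kaplan-Meier therefore describes a population in which nobody dies first. It is not the probability that a participant in this trial will receive new therapy. Participants are on the trial for 3 to 9 years (8.1), so such deaths are foreseeable.

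Two things are at stake. The first is the absolute level of the curves in each arm and in the Clinical Need Cohort. That cohort has no comparator, so its curve can only be read as an absolute risk. The second is how the superiority comparison is read. A hazard ratio for next treatment says nothing about deaths that came first, and the plan sets no companion analysis of those deaths beside it.

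**Working it through.** **Inputs from the protocol.** Section 18.1 gives a median PFS of about 4 years for the roughly 55% relapsed/refractory participants and about 10 years for the roughly 45% from FLAIR, with exponential distributions. Recruitment lasts 6 years, and the required events are expected about 3 years after it closes. There are 800 participants, 1:1, so 400 per arm.

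**Assumptions.** The documents give no figure for this endpoint. I take the PFS mixture as the distribution of the first event (next treatment, or death without it). A constant share *d* of first events are deaths, with *d* = 10%, 20% or 30%.

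**Step 1: reproduce the plan's figure.** S(t) = 0.45 × 2^(−t/10) + 0.55 × 2^(−t/4). Solving S(t) = 0.5 gives t = 5.84 years, as stated in 18.1.

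**Step 2: what each estimator targets.** With a constant share, the next-treatment hazard is (1 − d) times the total hazard. Then:

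- one minus Kaplan-Meier with deaths censored: 1 − S(t)^(1−d)
- probability of actually receiving next treatment: (1 − d) × (1 − S(t))

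**Step 3: numbers.** S(6) = 0.297 + 0.194 = 0.491. S(8) = 0.258 + 0.138 = 0.396.

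| d | 6 y: 1−KM | 6 y: incidence | Gap | 8 y: 1−KM | 8 y: incidence | Gap |
|---|---|---|---|---|---|---|
| 10% | 47.3% | 45.8% | 1.5 | 56.6% | 54.4% | 2.2 |
| 20% | 43.4% | 40.7% | 2.7 | 52.3% | 48.3% | 4.0 |
| 30% | 39.2% | 35.6% | 3.6 | 47.7% | 42.3% | 5.4 |

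A simulation with 400 per arm, uniform accrual over 6 years and a cut-off at year 9 gave the same gaps. At 6 years they are 0.52, 0.94 and 1.24 standard errors of the Kaplan-Meier estimate.

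**Step 4: the hazard ratio.** Censoring deaths in a Cox model yields a cause-specific hazard ratio for next treatment. Two illustrative cases, simulated with 20,000 per arm, show what it does and does not register.

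- *Deaths unrelated to treatment need.* The death hazard is doubled in one arm, from 0.02 to 0.04 per year. The hazard ratio for next treatment stays at about 1.0 (simulated 1.01), while for next treatment or death it is 1.18. The excess deaths are hidden but earn no credit.
- *Deaths among those who have failed and not yet started new therapy.* Failure rates are equal, but 30% against 10% of failures die in the gap. The hazard ratio is (1 − 0.30)/(1 − 0.10) = 0.78 (simulated 0.77) in favour of the arm with more such deaths. For next treatment or death it is 1.00. With 20% against 10% the ratio is 0.80/0.90 = 0.89.

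**The case against.** A cause-specific hazard ratio is a standard estimand, and the appended criteria define time to next treatment without death. Counting death as an event would make a different endpoint. It would be close to the event-free survival defined in the same part of Appendix 1, and it would overlap the primary endpoint. That stands, and it is why the composite belongs in a sensitivity analysis and should not replace the superiority test.

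A reader might infer that the censoring rule turns deaths into apparent benefit for pausing. The documents do not support this. The first case in Step 4 shows no such credit. The second needs more deaths in one arm among people who have stopped ibrutinib after failure and not yet started new therapy. No section gives such a rate or a difference between arms, and the distortion could favour either arm. What remains is a possibility. It is not far-fetched, because 17.4.8 names deaths between stopping ibrutinib and new treatment, and 12.5 links treatment failure to stopping ibrutinib and considering further therapy.

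Excess deaths would also show elsewhere. They count in the primary endpoint, which must meet the margin in both ITT and per-protocol populations (19.3), and in overall survival (19.4.1). This is a real safeguard for the trial's overall conclusion, but it does not correct the time-to-next-treatment curve or tell a reader how to interpret its hazard ratio.

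Finally, the gap is modest, the death share is assumed, and 19.4.7 promises curves without a landmark probability. At 8 years only about one sixth of each arm (about 67) could have been followed that long, and about 26 of them (67 × 0.396) would be event-free. In a Clinical Need Cohort of about 30, sampling error at 40% incidence is about 9 points (√(0.4 × 0.6/30)). All of this limits the size of the problem. The bias still runs in one direction and is avoidable, and a larger sample would not remove it.

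**Conclusion.** The point holds in two parts of different strength. The curves are certain to overstate the probability of receiving next treatment if any deaths come first. Under the protocol's PFS mixture and an assumed 10 to 30% share of deaths among first events, the excess is about 1.5 to 3.6 points at 6 years and 2.2 to 5.4 at 8 years. These sizes depend on that share and on using PFS to stand for the first event.

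The hazard ratio is valid as a cause-specific quantity. It hides an excess of deaths, and it misleads about benefit only under the condition described above, whose likelihood cannot be judged from the documents. A superiority claim on this endpoint should therefore not be read without the deaths beside it. This is a secondary endpoint, so the primary analysis and the 379 events are unaffected.

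**What to change.** In 17.4.8, state that death before next treatment is a competing event. In 19.4.7:

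- Replace the Kaplan-Meier curves with Aalen-Johansen cumulative incidence of next treatment and of death without next treatment, by arm and for the Clinical Need Cohort.
- Keep the Cox model, call its result a cause-specific hazard ratio, and report the cause-specific hazard ratio for death without next treatment next to it.
- Add time to next treatment or death as a sensitivity analysis, to be read before any claim of superiority.

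The cost is a change of wording and a little more analysis. The dates of death and of next treatment are already needed for existing endpoints, so no new data are required. The composite mixes deaths with treatment need and so dilutes an effect on treatment need alone, which is acceptable in a sensitivity analysis.
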